8.2.8. Infusion-Related Reactions

In order to mitigate the risk of IRRs, the study drug will be infused over approximately 2 hours for the first 2 doses in the study followed by close monitoring for approximately 2 hours at the investigative site.

Availability of resuscitation equipment must be ensured.

Any participant who has experienced a Grade 2 IRR, will continue with the approximate 2-hour infusion regimen (and approximately a 2-hour post infusion observation) for the duration of the study.

Participants who experience a Grade ≥ 3 IRR should be discontinued from the study.

Pre-medication with antihistamines or corticosteroids is not recommended at this time as a lower risk of occurrence for IRR is expected with the approximately 2-hour infusion time. However, based on emerging clinical experience, the sponsor may implement a premedication regimen for all future participants **if** >1 incidents of IRR Grade 2 is observed in Part A, or ≥ 1 incidents of IRR

Grade 2 is observed in Parts B or C. Such a premedication regimen would be administered approximately 30 minutes before the infusion of the study drug and will consist of an oral non-sedating H1 histamine blocker (eg, loratadine 10 mg orally or equivalent) and oral paracetamol (eg, acetaminophen 650 mg orally or equivalent).

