- n. Biopsy and tape strip samples to be collected pre dose. At Week 0, lesional and non lesional skin samples will be collected. At later timepoints, lesional skin samples will be collected.
- o. Participants who discontinue study intervention but do not terminate study participation are strongly encouraged to return for all protocol specified procedures for the safety follow up period and also for the ET Visit 5 weeks after last dose was administered. The procedures and evaluations listed for the ET visit should also be performed approximately 5 weeks after the last dose of study intervention. Participants who terminate study participation early should complete the procedures and evaluations listed for the ET visit approximately 5 weeks after their last administration of study intervention.
- p. Skin biopsy for all 10 participants of Part A and first 10 participants of Part B. At Week 0, lesional and non lesional skin samples will be collected. At Week 6, lesional skin samples will be collected.
- q. Skin biopsy for no participants in Part A, 20 last participants in Part B, and all participants in Part C. At Week 0, lesional and non lesional skin samples will be collected. At Week 16, lesional skin samples will be collected.

- r. Skin barrier function assessment should be evaluated together with tape stripping. Skin barrier function evaluation before tape stripping and after every 5 tapes.
- s. Vital signs (Heart rate, respiratory rate, temperature, blood pressure) to be collected every 30 mins between 0 to 4 hrs. This applies to the first 2 infusions only.
- t. For the first 2 doses, the study drug will be infused over approximately 2 hours to reduce the risk for IRR, followed by at least approximately a 2 hour observation. For the subsequent infusions, the infusion time may be decreased to approximately one hour with a minimum of approximately 1 hour observation period.
- u. Triplicate ECG to be done pre dose and post end of first infusion (after approximately 2 hours), at Week 0 only.
- v. Vital signs (heart rate, respiratory rate, temperature, blood pressure) to be collected approximately every 30 mins between 0 to 2 hours for infusions 3 through 15. This does not apply to the first 2 infusions.
- w. Additional serial TEWL, SCH, and EIS measurements will be acquired after every 5 tape strips at Weeks 0, 4, and 16.

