Infusion-related reactions	
IRR have been reported with the first or second IV infusions of bermekimab. In the largest oncology study, PT023 Version 3, there were reports of infusion reaction in 2.6% (11 of 430) participants compared to 0% in placebo. The majority (n=10) were mild to moderate (Grade 1 to 2) and did not result in discontinuation. There was one Grade 3 infusion reaction, an SAE that resulted in patient discontinuation.
	
In order to mitigate the risk of IRRs, the study drug will be infused over approximately 2 hours for the first 2 doses in the study followed by close monitoring for approximately 2 hours at the investigative site.
 
Availability of resuscitation equipment must be ensured.
 
Any participant who has experienced a Grade 2 IRR, will continue with the 2-hour infusion regimen (and a 2-hour post infusion observation) for the duration of the study.
 
Participants who experience a Grade ≥ 3 IRR should be discontinued from the study.
 
Pre-medication with antihistamines or corticosteroids is not recommended at this time as a lower risk of occurrence for IRR is expected with the approximately 2-hour infusion time. However, based on emerging clinical experience, the sponsor may implement a premedication regimen for all future participants if > 1 incidents of IRR Grade 2 is observed in Part A, or ≥ 1 incidents of IRR Grade 2 is observed in Parts B or C. Such a premedication regimen would be administered approximately 30 minutes before the infusion of the study drug and will consist of an oral non-sedating H1 histamine blocker (eg, loratadine 10 mg orally or

Table 1: Benefit-Risk for Study Participants (Bermekimab)		
Potential Risks of Clinical Significance	Summary of Data/ Rationale for Risk	Mitigation Strategy
Serious hypersensitivity reactions (including anaphylaxis and serum sickness).	Serious hypersensitivity reactions (including anaphylaxis and serum sickness) may occur at any time and not only during administration of bermekimab.	equivalent) and oral paracetamol (eg, acetaminophen 650 mg orally or equivalent). Study intervention must not be administered to individuals with known or suspected intolerance or hypersensitivity to any biologic medication or known allergies or clinically significant reactions to any components of the formulation used in this study.

IgG immunoglobulin G; IL interleukin; IRR infusion related reactions; TB tuberculosis.

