8.2.2. Vital Signs

Temperature, pulse/heart rate, respiratory rate, blood pressure will be obtained prior to study intervention administration at visits specified in the schedule of activities.

In addition, all participants will have an extended in-clinic observation period of approximately 4 hours during the first 2 infusions. In this period, vital signs will be taken at the following time points: 0 hour (start of infusion), 30 minutes, 1 hour, 1 hour and 30 mins, 2 hours (end of infusion), 2 hours and 30 mins, 3 hours, 3 hours and 30 mins, and 4 hours (post-infusion). Beyond the first 2 infusions, all participants will have approximately a 1 hour infusion period and at least a 1 hour observation post infusion, as well as vital signs taken every 30 minutes.

Blood pressure and pulse/heart rate measurements should be preceded by approximately 5 minutes of rest in a quiet setting without distractions (eg, television, cell phones).

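### After a Grade 2 infusion reaction, the protocol's infusion, observation and vital-sign timings disagree, and the Schedule of Activities schedules no reading after the end of a 2-hour infusion

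*Protocol*

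**What the plan says.** **The rule after a Grade 2 reaction.** Protocol 8.2.8 says that a participant who has had a Grade 2 IRR "will continue with the approximate 2-hour infusion regimen (and approximately a 2-hour post infusion observation) for the duration of the study". Table 1 in 2.3.1 repeats the rule: such a participant "will continue with the 2-hour infusion regimen (and a 2-hour post infusion observation) for the duration of the study". Participants with Grade 3 or higher reactions are to be discontinued from the study (7.1, 8.2.8, Table 1).

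**The general rule.** Protocol 8.2.2: "Beyond the first 2 infusions, all participants will have approximately a 1 hour infusion period and at least a 1 hour observation post infusion". The same sentence adds vital signs at 30-minute intervals and gives no end time. The synopsis (1.1), protocol 4.1 and SAP 1.2 carry the same general rule. None states an exception or points to 8.2.8.

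**The SoA footnotes (1.3).**
- Footnote s sets vital signs every 30 minutes from 0 to 4 hours: "This applies to the first 2 infusions only".
- Footnote t permits, but does not require, shortening later infusions to about one hour, and it states the 1-hour observation as a minimum.
- Footnote v, for infusions 3 through 15, sets vital signs "to be collected approximately every 30 mins between 0 to 2 hours".

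Table 2 (6.1) schedules weekly infusions from Week 0 through Week 15.

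**The concern.** There are two conflicts. First, 8.2.8 and Table 1 prescribe one infusion and observation time for a participant with a Grade 2 reaction, while 1.1, 4.1 and 8.2.2 prescribe another for everyone. Second, the vital-sign window in footnote v fits the 1-hour regimen and has no counterpart for the longer one.

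The extended infusion and observation are the protocol's stated mitigation for a named risk. Because worse reactions lead to discontinuation, Grade 2 is the worst IRR grade among participants meant to continue dosing. Symptomatic hypotension defined by systolic pressure is one of the triggers for stopping study intervention (7.1, 8.2.7). Followed literally, footnote v gives a participant who has already reacted fewer scheduled readings after the infusion than one who has not.

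There is also a reporting consequence. SAP 5.6.4 lists participants with markedly abnormal vital signs. What reaches that listing depends on when readings are taken, and with the passages in conflict, sites may reasonably differ on that.

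**Working it through.** This is timeline arithmetic. The window is infusion time plus observation time, and the number of readings on a 30-minute grid is window ÷ 0.5 h + 1.

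**Step 1. Reproduce the protocol's own schedules.**
- First two infusions: 2 h + 2 h = 4 h, and 4 ÷ 0.5 + 1 = 9 readings. This matches the nine time points listed in 8.2.2 (0, 0.5, 1, 1.5, 2, 2.5, 3, 3.5 and 4 h).
- Later infusions on the general rule: 1 h + 1 h = 2 h, and 2 ÷ 0.5 + 1 = 5 readings. This matches footnote v's window. It was evidently built for the 1-hour regimen.

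**Step 2. Apply footnote v to each regimen.**

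| Regimen, infusions 3 to 15 | Infusion ends | Readings under footnote v | After end of infusion |
|---|---|---|---|
| 1 h + 1 h (8.2.2) | 1 h | 0, 0.5, 1, 1.5, 2 h | 2 (1.5 and 2 h) |
| 2 h + 2 h (8.2.8) | 2 h | 0, 0.5, 1, 1.5, 2 h | 0 |

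On the 8.2.8 regimen the points at 2.5, 3, 3.5 and 4 h are not scheduled: 9 − 5 = 4 of 9.

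**Step 3. Count per affected participant.** Footnote v covers infusions 3 through 15, which is 15 − 3 + 1 = 13 infusions. If the Grade 2 reaction occurs at infusion 1 or 2 (Table 1 says such reactions have been reported with the first or second infusion), up to 13 × 4 = 52 grid points are unscheduled. If it occurs at a later infusion k, the count is 4 × (15 − k).

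**Step 4. Compare the ways a site could combine the texts.**
- 8.2.8 with footnote v: 2-hour infusion, 5 readings, none during the 2-hour observation apart from the one at its start.
- 8.2.8 with the open-ended 30-minute interval in 8.2.2: 2-hour infusion, 9 readings.
- 8.2.2 with footnote v: 1-hour infusion, 5 readings covering the whole period, but 8.2.8 is not followed.

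**Step 5. Check the infusion range.** Week 0 through Week 15 is 15 − 0 + 1 = 16 infusions. Footnotes s (infusions 1 and 2) and v (3 to 15) cover 2 + 13 = 15. Infusion 16, at Week 15, has no footnote window on either regimen.

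**Step 6. How many participants?** Table 1 reports infusion reactions in 11 of 430 in the largest oncology study, of which 10 (10 ÷ 430 = 2.3%) were Grade 1 or 2. The Grade 2 share is not given. If every one of those 10 were Grade 2, and if the rate carried over to the 48 planned active participants (8 + 24 + 16), the expected number would be 48 × 10 ÷ 430 = 1.1. If none were, it would be 0. The range 0 to 1.1 is only illustrative, because 4.2.1 says that the dose levels and frequency here exceed those previously studied.

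**The case against.** The strongest reply is that 8.2.8 is the dedicated IRR section, that Table 1 states the same rule, and that a specific safety rule is normally read as an exception to a general description. That is a fair way to settle infusion and observation time. It does not settle vital signs: 8.2.8 sets no vital-sign schedule, footnote s expressly excludes later infusions from the 4-hour window, and footnote v makes no exception.

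A reader might infer several stronger points, which the documents do not support:

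- *That the SoA imposes a 1-hour infusion on everyone.* Footnote t is permissive, its observation time is a minimum, and it is compatible with 8.2.8. The unconditional wording is in 1.1, 4.1 and 8.2.2.
- *That 8.2.2 also ends vital signs at 2 hours.* It gives no end time and can be read to cover a longer observation. The gap rests on footnote v alone.
- *That these participants go unmonitored, or that readings are lost.* The in-clinic observation in 8.2.8 still applies, 8.2.7 calls for careful observation of all participants, the end-of-infusion reading is scheduled, and the hypotension trigger requires symptoms, which would be expected to prompt a measurement. The accurate term is unscheduled.
- *That 14 infusions and 56 readings are affected.* That count takes 16 − 2 = 14 infusions, but footnote v stops at infusion 15. Infusion 16 is a separate omission.
- *That at most about one participant would be affected.* The 10 of 430 combines Grades 1 and 2 and comes from an oncology study, so 1.1 is not an upper bound.
- *That these are the highest-risk participants.* The documents show only that Grade 2 is the worst IRR grade among those meant to continue dosing.

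**Conclusion.** The inconsistency is real. Protocol 8.2.8 and Table 1 conflict with the synopsis, 4.1 and 8.2.2 on infusion and observation time after a Grade 2 IRR. Even if 8.2.8 is taken to govern, footnote v followed literally leaves 4 of the 9 points on the 4-hour grid unscheduled at each extended infusion, all of them after the end of infusion. That is up to 52 per affected participant if the reaction comes at infusion 1 or 2. The count assumes that sites follow 8.2.8 for timing and footnote v for vital signs, and that dosing continues through infusion 15. Under the open-ended wording in 8.2.2 there would be no shortfall, which is itself a reason to reconcile the texts. The number of participants affected is probably small but cannot be bounded from the documents. Separately, footnote v omits the last of the 16 planned infusions.

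No planned efficacy inference is touched. Since the SAP reports that the sponsor ended the study early and that only listings will be produced, the practical value of the correction is mainly for any continued or reused protocol text.

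**What to change.** Reconcile the synopsis (1.1), SoA footnotes s, t and v (1.3), Table 1 (2.3.1), 4.1, 8.2.2 and 8.2.8 so that infusion time, observation time and the vital-sign window after a Grade 2 IRR agree wherever they appear. Align footnote v's infusion range with the 16 planned infusions, and settle whether the 30-minute interval in 8.2.2 is bounded by footnote v. If the SAP is reissued, carry the agreed wording into its 1.2. Which infusion, observation or monitoring rule applies is for the sponsor's clinical team; this point does not choose one.

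The cost is a few words of protocol and footnote text plus a clarification to sites. Any change in the number of readings would depend on how the clinical team resolves the conflict.

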Data that may potentially unblind the intervention assignment (ie, study intervention serum concentrations, anti-JNJ-77474462 antibodies, study intervention preparation/accountability data, intervention allocation) will be handled with special care to ensure that the integrity of the blind is maintained and the potential for bias is minimized. This can include making special provisions, such as segregating the data in question from view by the investigators, clinical team, or others as appropriate until the time of DBL and unblinding.

Under normal circumstances, the blind should not be broken until all participants have completed the study and the database is finalized. Otherwise, the blind should be broken only if specific emergency intervention/course of action would be dictated by knowing the intervention status of the participant. In such cases, the investigator may in an emergency determine the identity of the intervention by contacting the IWRS. While the responsibility to break the intervention code in emergency situations resides solely with the investigator, it is recommended that the investigator contact the sponsor or its designee if possible to discuss the particular situation, before breaking the blind. Telephone contact with the sponsor or its designee will be available 24 hours per day, 7 days per week. In the event the blind is broken, the sponsor must be informed as soon as possible. The date and reason for the unblinding must be documented in the appropriate section of the eCRF and in the source document. The documentation received from the IWRS indicating the code break must be retained with the participant's source documents in a secure manner.

For the purpose of the interim analysis of safety data and preliminary PK, efficacy, and PD analysis, designated sponsor personnel will be unblinded to the relevant data as is required (Section 8.4, Pharmacokinetics and Immunogenicity). The randomization code will be disclosed to those authorized and only for those participants included in the interim analysis. All site personnel and participants will remain blinded to the treatment assignments until the last participant completes the Week 20 evaluations and the final database is locked.

Participants who have had their intervention assignment unblinded should continue to return for scheduled evaluations and are not eligible to receive further study intervention.

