7. DISCONTINUATION OF STUDY INTERVENTION AND PARTICIPANT DISCONTINUATION/WITHDRAWAL

7.1. Discontinuation of Study Intervention

A participant's study intervention must be discontinued if:

- The participant withdraws consent to receive study intervention.
- The investigator believes that for safety reasons or tolerability reasons (eg, AE) it is in the best interest of the participant to discontinue study intervention
- Participants who experience a Grade ≥ 3 IRR should be discontinued from the study
- The participant has a serious adverse reaction that is related to an infusion of the study drug administration including a hypersensitivity reaction resulting in bronchospasm, wheezing and/or dyspnea that requires ventilatory support OR that results in symptomatic hypotension with a decrease in systolic blood pressure of 30% from a participant's baseline value or systolic blood pressure <90 mm Hg ([Sampson 2006](#)). In general, discontinuation of study intervention administration must be considered for participants who develop a nonserious but severe infusion-related reaction.
- The participant has a reaction resulting in myalgia and/or arthralgia with fever and/or rash (suggestive of serum sickness and not representative of signs and symptoms of other recognized clinical syndromes) occurring 1 to 14 days after an infusion of study intervention. These may be accompanied by other events including pruritus, facial, hand, or lip edema, dysphagia, urticaria, sore throat, and/or headache.
- The participant becomes pregnant or plans a pregnancy during the study period. Refer to [Section 10.5](#), Appendix 5: Contraceptive and Barrier Guidance.
- The initiation of protocol-prohibited medications, treatments, or interventions (outlined in [Section 6.8](#), Concomitant Therapy) that have an impact on AD efficacy evaluations.
- The participant has a malignancy including squamous cell skin cancer. Consideration may be given to allow participants, who develop ≤ 2 basal cell skin cancers and who are adequately treated with no evidence of residual disease, to continue to receive study intervention.
- A systemic opportunistic infection.
- A recurrent or chronic serious infection.
- The participant is deemed ineligible according to the following TB screening criteria:
 - A diagnosis of active TB is made.

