 - A participant has symptoms suggestive of active TB based on follow-up assessment questions and/or physical examination or has had recent close contact with a person with active TB and cannot or will not undergo additional evaluation.
 - A participant undergoing evaluation has a chest radiograph with evidence of current active TB and/or a positive QuantiFERON-TB test result and/or 2 indeterminate QuantiFERON-TB test results on repeat testing (refer to [Section 8.2.9](#), Tuberculosis Evaluations) (and/or a positive tuberculin skin test result in countries in which the QuantiFERON-TB test is not approved/registered or the tuberculin skin test is mandated by local health authorities).

- A participant receiving treatment for latent TB discontinues this treatment prematurely or is noncompliant with the therapy.
- The participant is unable to adhere to the study visit schedule or comply with protocol requirements.
- Abnormal liver tests as outlined in Section 10.7, Appendix 7: Liver Safety: Suggested Actions and Follow-Up Assessments.
- Use of prohibited corticosteroids:
 - IM and IV formulations
 - Oral corticosteroids for more than 10 days.
- The participant has his/her treatment assignment unblinded by the investigator.
- Sponsor decision.

If a participant discontinues study intervention for any reason before the end of the double-blind phase, then the end-of-intervention assessments should be obtained and scheduled assessments off study intervention should be continued. Study intervention assigned to the participant who discontinued study intervention may not be assigned to another participant. Additional participants will not be entered.

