Participants who decide to discontinue study intervention administration for reasons other than those outlined above must be interviewed by the investigator to determine if a specific reason for discontinuing study intervention can be identified. Participants should be explicitly asked about the possible contribution of AEs to their decision to discontinue study intervention; investigators should confirm that any AE information elicited has been documented. If a participant elects to discontinue study intervention due to an AE, the event should be recorded as the reason for study intervention discontinuation, even if the investigator's assessment is that the AE would not require study intervention discontinuation. The reason for study intervention discontinuation must be documented in the eCRF and in source documents. Study intervention assigned to a participant who discontinues may not be assigned to another participant.

A participant will not be automatically withdrawn from the study if he or she must discontinue treatment before the end of the treatment regimen. Participants who discontinue study intervention but do not terminate study participation are strongly encouraged to return for all protocol-specified procedures and evaluations for approximately 5 weeks following the last dose of study intervention. The procedures and evaluations listed for the early termination visit should also be performed approximately 5 weeks after the last dose of study intervention.

All procedures and evaluations must be conducted prior to a participant's withdrawal of consent.

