8.2.7. Allergic Reactions

Before any IV infusion, appropriately trained personnel and medications must be available to treat allergic reactions, including anaphylaxis. All participants must be observed carefully for symptoms of an allergic reaction (eg, urticaria, itching, hives). If a mild or moderate allergic reaction is observed, acetaminophen, non-steroidal anti-inflammatory drugs, and/or diphenhydramine may be administered.

In the case of a severe allergic reaction (eg, anaphylaxis), IM or SC aqueous epinephrine, corticosteroids, respiratory assistance, and other proper resuscitative measures may be essential and must be available at the location where the infusions are being administered.

Participants who experience serious adverse reactions related to an infusion should be discontinued from further study intervention administrations.

Participants who experience reactions following an infusion that result in bronchospasm, wheezing and/or dyspnea that requires ventilatory support, or that results in symptomatic hypotension with a decrease in systolic blood pressure of 30% from a participant's baseline value blood or systolic blood pressure <90 mm Hg will not be permitted to receive additional study intervention ([Sampson 2006](#)).

Participants who experience reactions suggestive of serum sickness-like reactions (resulting in symptoms such as myalgia and/or arthralgia with fever and/or rash that are not representative of signs and symptoms of other recognized clinical syndromes) occurring 1 to 14 days after an infusion of study intervention, should be discontinued from further study intervention administrations. Note that these symptoms may be accompanied by other events including pruritus, facial, hand, or lip edema, dysphagia, urticaria, sore throat, and/or headache.

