Participants who experience close contact with an individual with active TB during the conduct of the study must have a repeat chest radiograph, a repeat QuantiFERON-TB (or T-SPOT for sites in Japan) test, a repeat tuberculin skin test in countries in which the QuantiFERON-TB test is not approved/registered or the tuberculin skin test is mandated by local health authorities, and, if possible, referral to a physician specializing in TB to determine the participant’s risk of developing active TB and whether treatment is warranted. Study intervention administration should be interrupted during the investigation. A positive QuantiFERON-TB (or T-SPOT for sites in Japan) test or tuberculin skin test result should be considered detection of latent TB. Participants with a newly identified positive QuantiFERON-TB (or T-SPOT for sites in Japan or tuberculin skin) test result must undergo an evaluation to rule out active TB and initiate appropriate treatment for latent TB. Appropriate treatment for latent TB is defined according to local country guidelines for immunocompromised participants. If no local country guidelines for immunocompromised participants exist, US guidelines should be followed, or the participant will be excluded from the study. If the QuantiFERON-TB test result is indeterminate, the test should be repeated. For sites in Japan, a participant whose first T-SPOT test result is borderline should have the test repeated. Participants should be encouraged to return for all subsequent scheduled study visits according to the protocol. Participants who discontinue treatment for latent TB prematurely or who are noncompliant with therapy must immediately discontinue further administration of study

intervention and be encouraged to return for all subsequent scheduled study visits according to the SoA (Section 1.3).

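### The rule for Grade 3 or higher infusion reactions says to leave the study where the rest of the protocol stops only the drug, and the 5-week follow-up text does not secure the Week 16 EASI (minor)

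*Protocol*

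**What the plan says.** **Removal rule.** Section 8.2.8, the infusion-reaction row of Table 1 (Section 2.3.1) and a bullet in Section 7.1 all state that a participant with a Grade 3 or higher "IRR should be discontinued from the study".

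**Rules that stop only the drug.**
- The 7.1 list containing that bullet opens by saying when a participant's "study intervention must be discontinued if". The next bullet asks only that stopping study intervention be considered for a severe but non-serious infusion reaction.
- Later in 7.1: "A participant will not be automatically withdrawn from the study if he or she must discontinue treatment".
- Section 7.2 gives three reasons for withdrawal from the study: loss to follow-up, withdrawal of consent and death.
- Section 8.2.7: "Participants who experience serious adverse reactions related to an infusion should be discontinued from further study intervention administrations".

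**Follow-up after stopping drug.**
- Section 7.1, for discontinuation for any reason before the end of the double-blind phase: "scheduled assessments off study intervention should be continued".
- Two other sections point the same way. Unblinded participants (6.3) "should continue to return for scheduled evaluations and are not eligible to receive further study intervention". Participants who stop latent-TB treatment (8.2.9.2) are to "be encouraged to return for all subsequent scheduled study visits according to the" schedule.
- A later paragraph of 7.1 strongly encourages return for roughly 5 weeks after the last dose and places the early termination (ET) visit there. Footnote o encourages return for the safety follow-up procedures and an ET visit at the same time.

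**Analysis.** In Section 9.4.2, Table 4 uses observed data after ICE 4, which is stopping drug for reasons other than lack of efficacy or worsening AD. A participant without a Week 16 evaluation is a non-responder. SAP 5.3.2 and Appendix 2 replace all formal analyses with listings.

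**The concern.** A serious Grade 3 infusion reaction falls under two rules: 8.2.7 stops dosing, and 8.2.8 ends participation. Both are worded as recommendations, so neither clearly overrides the other.

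The same kind of conflict affects anyone who stops drug early for an ICE 4 reason. One paragraph of 7.1 keeps the schedule going. The later paragraph and footnote o, read alone, take a site to about 5 weeks after the last dose and no further.

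Two things are at stake. The first is follow-up of a participant who has just had a severe reaction. The second is the estimand: treatment policy for ICE 4 needs an observed Week 16 EASI. If none is collected, the missing-data rule scores non-response, and ICE 4 is in effect handled by the composite rule meant for ICEs 1 to 3.

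**Working it through.** **1. When the 5-week text falls short of Week 16.** Dosing runs from Week 0 to Week 15, which is 16 dosing weeks. With last dose at Week w, the ET visit is at about Week w + 5. This is before Week 16 when w ≤ 10, so for 11 of 16 possible last-dose weeks. Table 1 reports infusion reactions at the first or second infusion, which puts the ET visit near Week 5 or 6.

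**2. Reproducing the plan's power.** Inputs from Section 9.2: 24 (1200 mg), 16 (dose C) and 12 (pooled placebo); Fisher's exact test, two-sided 0.10; 15% vs 65% and 15% vs 70%.

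Power = Σx Σy Bin(x; n, p_active) · Bin(y; 12, p_placebo) · 1{test rejects}, with rejection at 0.05 in each tail.
- 24 vs 12, 15% vs 65%: 85.1% (protocol 85%).
- 16 vs 12, 15% vs 70%: 86.1% (protocol 86%).

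Eight of the nine rows of protocol Table 3 agree within 2 points. The exception is n = 16 at 12% vs 65%: 85.4% against 83%. The usual two-sided Fisher p-value gives 90.2% and 89.0% for the two rows above.

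**3. Event rate (an assumption).** The largest oncology study treated 430 participants: "There was one Grade 3 infusion reaction, an SAE that resulted in patient discontinuation". So 1/430 = 0.23%, exact 95% interval 0.006% to 1.29%. Dose, schedule and population may differ here. In the 24 + 16 = 40 active participants in the tested groups, the chance of at least one event is 1 − (1 − 1/430)^40 = 8.9% (0.2% to 40.5% at the interval limits).

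**4. What the wording costs.** The participant is off drug under either wording. The fair comparison is therefore a Week 16 EASI observed off drug against one scored as non-response. Assume the off-drug response equals the placebo rate, 15%.

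At rate r the active response is p(1 − r) if scored as non-response and p(1 − r) + 0.15r if observed. With one participant affected, the other n − 1 respond at p and that one responds at 0 or at 0.15.

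| Scenario | 1200 mg: scored → observed | Dose C: scored → observed |
|---|---|---|
| r = 1/430 | 84.90% → 84.95% (0.05) | 85.91% → 85.96% (0.05) |
| r = 1.29% | 83.8% → 84.1% (0.3) | 84.9% → 85.2% (0.3) |
| one participant affected | 81.03% → 81.98% (about 1.0) | 80.43% → 81.65% (1.2) |

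With the usual two-sided Fisher p-value, the one-participant gains are 0.7 and 1.1 points.

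**5. ICE 4 in general.** The documents give no rate of early discontinuation, so no size follows from them. As a sensitivity only, take 24 vs 12, 15% off-drug response, and 2%, 5% or 10% with ICE 4 and no Week 16 EASI, in the active arm alone. Observed vs scored power is 83.6 vs 83.1, 81.1 vs 79.8 and 76.5 vs 73.5, a loss of 0.5 to 3.0 points. With the same shares scored as non-response in both arms, power is 83.7, 81.4 and 77.4, so there is no loss.

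**The case against.** The strongest reply is that the protocol already gives the right answer. The bullet sits in a study-intervention list. Section 7.1 continues scheduled assessments after discontinuation for any reason, and 7.2 has no infusion-reaction reason. Section 6.8.4 uses the same loose phrase about failed rescue therapy, which suggests drafting habit. Five weeks after the last dose also mirrors the planned gap from Week 15 to Week 20, so it may be a safety minimum that does not say visits then stop. Much of this stands: a site reading the whole of 7.1 would collect the Week 16 EASI. It does not remove the conflict, because the removal sentence appears in three places, including the section a site would consult during a reaction.

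A reader might infer that the protocol takes early discontinuers out before Week 16. It does not; the continuing-assessments sentence says the opposite. A reader might also treat 7.1 as cleanly stopping only drug, but it repeats the removal sentence itself.

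The drop from 85.1% to 81.0% (1200 mg) or 86.1% to 80.4% (dose C) with one participant affected might be blamed on the wording. Most of it is lost drug effect, which no wording restores.

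Even the small gain may not arise. If IM or IV corticosteroids given for a severe reaction (8.2.7, 6.8.3) count as ICE 2, or later AD treatment counts as ICE 2 or 3, the participant is already a non-responder. The same holds for a true non-responder 15 to 16 weeks after the last dose of a drug with a half-life of about 1 week.

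**Conclusion.** The inconsistency is real and minor. The removal sentence conflicts with the 7.1 list opening, the no-automatic-withdrawal statement, 7.2 and 8.2.7. The 5-week text does not match the continuing-assessments sentence in the same section. A site following either text alone could lose the Week 16 EASI and the scheduled follow-up after a severe reaction.

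The gain from correcting it for infusion reactions is about 0.05 power points at the assumed rate, and about 1 point if one participant in a group is affected. Planned power stays above 80% in every infusion-reaction scenario calculated. These figures rest on the oncology rate carrying over and on 15% response off drug.

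A reader might extend this to a material loss of power from ICE 4 generally. The documents do not support that: they give no discontinuation rate, and the loss disappears if missingness is equal in both arms. Because the SAP lists the data and tests nothing, the point concerns the protocol-planned analysis and participant follow-up, not a reported result.

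**What to change.** - In Table 1, the 7.1 bullet and 8.2.8, replace removal from the study with discontinuation from study intervention.
- In the later paragraph of 7.1 and in footnote o, state that, unless consent is withdrawn, participants off study intervention continue scheduled efficacy and safety assessments, including the Week 16 EASI, in line with the continuing-assessments sentence in 7.1.
- Keep the ET visit about 5 weeks after the last dose for safety, PK and antibody sampling.
- State that post-baseline biopsies and tape strips are not required once drug is stopped. Otherwise continuing the full schedule would impose the Week 6 or Week 16 biopsies on someone off drug after a severe reaction.
- The same edit in 6.8.4 is optional. It does not affect the primary endpoint, because rescue is already ICE 3.

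Cost: wording in five places. The visits are already in the schedule; the burden is extra visits for a few participants off treatment.
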